##### **8.1.5.1 Extent of exposure**

For each of the drugs duration of administration (number of days) and administered dose will be reported as absolute number and percentage of planned duration and dose. Number of interruptions and duration of interruptions will be reported.

##### **8.1.5.2 Dose limiting toxicities (DLT)**

All dose limiting toxicities will be listed separately per dose level, including description of the event, date of first administration of cytarabine, date of first administration of venetoclax, date of last administration of cytarabine drug, date of last administration of venetoclax, date of onset of AE, date of end of AE, severity, seriousness, relatedness to either venetoclax or cytarabine, action taken and outcome

Incidences of DLTs will be reported with counts and percentage grouped by CTCAE toxicity grade, dose level, severity, outcome, related study drug and overall.

##### **8.1.5.3 Adverse events**

Adverse events occurring before the first administration of venetoclax will be assigned to the medical history and analyzed in that context.

Incidences of AEs will be reported with counts and percentage grouped by CTCAE toxicity grade, dose level, severity, relatedness to cytarabine, relatedness to venetoclax and overall. AEs leading to discontinuation, SAEs, and deaths will be listed as described for DLTs in section [8.1.5.2](#).

##### **8.1.5.4 Laboratory parameters**

Laboratory parameters will be analyzed descriptively and separately for each time point. Additionally the parameters will be classified as “normal” / “abnormal, not clinically significant” / “abnormal, clinically significant” and change tables will be calculated comparing V1 with V8–EOT.

## **8.2 Phase II – Expansion part**

### **8.2.1 Sample size**

In combination with low-dose cytarabine, the bcl2 inhibitor venetoclax has shown promising clinical activity with a CR+CRi rate of 54% in a frail elderly patient population receiving initial treatment for newly diagnosed AML(Wei et al., J Clin Oncol 2019). In addition, cytarabine may synergize with venetoclax by down-regulating Mcl-1. In a paper from 2011, Touzeau et al. showed synergy between ABT-737 and Ara-C in mantle cell lymphoma cell lines (Touzeau et al., Clin Cancer Res 2011).

We hypothesize that the combination of intermediate-dose cytarabine salvage plus venetoclax will have an increased antileukemic efficacy compared to standard salvage alone and that efficacy signals can already be shown in a small patient number in a phase-I/II expansion cohort. Historical data show: While only around 20% of frail patients who have been treated with low –dose cytarabine alone reach CRs, the combination with venetoclax results in an increase by 30% (Burnett 2007). Standard intensive relapse treatments produce CR rates of around 40-55% (Steinmetz et al., Ann Hematol 1999; Karanes et al., Leuk Res 1999; Pastore et al., Ann Hematol 2003; Larsson et al., Leukemia & Lymphoma 2012; Fiegl et al., Leukemia 2014; Ahmed et al., Leuk Res 2015; Thiel et al., Ann Oncol 2015; Bergua et al., Br J Haematol 2016). Assuming a similar beneficial effect of venetoclax in this setting, we assume a CR rate of 65% for the combination treatment of intermediate-dose cytarabine, mitoxantrone and venetoclax.

The phase II part will be performed as single stage study according to A'Hern (A'Hern Stat Med 2001). It will test the null hypothesis that the CR/CRi rate is  $\leq 45\%$ . This benchmark for the CR/CRi rate was selected based on literature review of trials for this patient population. We expect a CR/CRi rate of 65% with the combination treatment as the minimum required level of efficacy. This expectation is based on CR/CRi rates reported for the combination of venetoclax and demethylating agents in patients with de novo AML being around 70% (DiNardo ASH 2015, Pollyea ASCO 2016). To be able to reject the null hypothesis ( $H_0: p \leq 0.45$ ) in favor of the alternative hypothesis ( $H_1: p \geq 0.65$ ) at a one-sided significance level of 5% with 80% power 42 patients must be enrolled.

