**6.4.2.2 Remission assessment**

Remission assessment will follow standard criteria according to Döhner et al., 2017 and will be done 28-45 days after start of V-MAC (depending of blood count recovery), but has to be done latest on day 45 irrespective of the blood count regeneration.

If regeneration blasts are suspected, bone marrow aspiration should be repeated, but not later than day 45 from start of V-MAC. Only the final remission assessment will be documented in the eCRF.

To define the real number of platelets and neutrophils, a period of at least 2 days without transfusion or treatment with G-CSF is necessary to determine a CR or CRi.

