**Complete remission with incomplete recovery (CRi):**

All CR criteria are fulfilled except for residual neutropenia (granulocyte count  $\leq 1000/\mu\text{l}$ ) and/or thrombocytopenia (platelet count  $\leq 100.000/\mu\text{l}$ ).

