## **8.2.3 Definition of endpoints**

### **8.2.3.1 Primary endpoint CR/CRi rate**

The CR/CRi rate is the primary endpoint of the phase II expansion part. It is determined as follows: number of patients who achieved CR or CRi, divided by the number of all patients in the analysis set.

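### The protocol does not show that the 45% null is a CR/CRi rate for standard salvage: every salvage figure it gives is labelled CR

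*Protocol*

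**What the plan says.** The phase II primary endpoint (Protocol 8.2.3.1) is the "number of patients who achieved CR or CRi, divided by the number of all patients in the analysis set". Section 8.2.1 sets the null on that scale: "It will test the null hypothesis that the CR/CRi rate is" at most 45%. Its source is given as follows: "This benchmark for the CR/CRi rate was selected based on literature review of trials for this patient population". No CR/CRi figure for standard salvage follows.

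The evidence shown for standard salvage in the same section is that "Standard intensive relapse treatments produce CR rates of around 40-55" per cent. The synopsis and sections 1.1 and 1.4 give the same range, also labelled CR.

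The target rate has two labels within 8.2.1. First, "we assume a CR rate of 65% for the combination treatment of intermediate-dose cytarabine, mitoxantrone and venetoclax". Then, a paragraph later, "We expect a CR/CRi rate of 65% with the combination treatment as the minimum required level of efficacy".

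Section 6.4.2.2 defines CRi thus: "All CR criteria are fulfilled except for residual neutropenia" and/or thrombocytopenia. The marrow assessment "has to be done latest on day 45 irrespective of the blood count regeneration". The synopsis gives the decision rule: 25 CR/CRi among 42 patients rejects the null, with a one-sided 5% error and 80% power.

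**The concern.** CR/CRi contains CR, so in any cohort the CR/CRi rate is at least as high as the CR rate. If 45% was read off CR-only rates, trial patients are judged on a wider definition of success than the historical ones. The error would then run one way, in favour of V-MAC.

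The difference between the two measures could matter here. CRi as defined sets no minimum count recovery, and the response is read by day 45 whatever the counts.

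What is at stake is the meaning of a positive result. Section 8.2.1 frames the hypothesis as greater antileukaemic efficacy than standard salvage alone. Rejecting p ≤ 0.45 supports that only as far as 45% represents the CR/CRi rate of standard salvage.

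**Working it through.** **Inputs from the protocol.** n = 42 and cut-off 25 (synopsis); p0 = 0.45, p1 = 0.65, one-sided 5%, 80% power (8.2.1); historical range 40-55%, labelled CR (8.2.1).

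**Formula.** Exact binomial tail: P(X ≥ r | n, p) = Σ from k = r to n of C(n,k) p^k (1−p)^(n−k).

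**Step 1: reproduce the design.**
- P(X ≥ 25 | 42, 0.45) = 0.0415, the actual level.
- P(X ≥ 25 | 42, 0.65) = 0.8182, the power.
- A cut-off of 24 gives level 0.077; a cut-off of 26 gives power 0.723.
- A search over n confirms 42 as the smallest sample size that meets both requirements.

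The design is arithmetically correct for the null as stated.

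**Step 2: compare the labels.**

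| Item | Value | Label in the protocol |
|---|---|---|
| Primary endpoint (8.2.3.1) | – | CR or CRi |
| Null (8.2.1) | 45% | CR/CRi |
| Standard salvage (8.2.1) | 40-55% | CR |
| Target, first mention (8.2.1) | 65% | CR |
| Target, second mention (8.2.1) | 65% | CR/CRi |
| Venetoclax plus low-dose cytarabine (1.4) | 54% | CR+CRi |
| Low-dose cytarabine alone (1.4) | about 20% | CR |

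The last two rows are set against each other in section 1.4 to derive the expected gain, so the rationale mixes the two labels there as well.

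**Step 3: how often does a regimen that only equals standard salvage pass?** Let q be the true CR/CRi rate of standard salvage. The documents do not give q, so it is varied as an assumption.

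| Assumed q | Example | P(X ≥ 25 given 42, q) |
|---|---|---|
| 40% | low end of the range, already CR/CRi | 0.8% |
| 45% | 40% CR + 5 points CRi | 4.2% |
| 47.5% | midpoint of the range, already CR/CRi | 8.0% |
| 50% | 45% CR + 5 points CRi | 14.0% |
| 55% | 45% CR + 10 points CRi | 33.4% |

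Solving P(X ≥ 25 | 42, q) = 0.05 gives q ≈ 0.457. There is therefore less than one percentage point of slack above the 45% null.

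**Step 4: what a different benchmark would mean, keeping p1 = 0.65 and one-sided 5%.**

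| p0 | Cut-off at n = 42 | Power at n = 42 | Smallest n for 80% power (cut-off) |
|---|---|---|---|
| 0.45 | 25 | 81.8% | 42 (25) |
| 0.475 | 26 | 72.3% | 53 (32) |
| 0.50 | 27 | 60.8% | 69 (42) |
| 0.55 | 29 | 35.4% | 150 (93) |

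**The case against.** The protocol calls 45% a benchmark for CR/CRi, and it uses CR loosely elsewhere. Section 3.3 says the 42 patients inform the CR rate of the combination although the endpoint is CR/CRi, and the 65% carries both labels. The 40-55% may therefore already include CRi. This stands. A reader might infer that CRi patients count for V-MAC but not for the historical patients; the documents do not establish that, and the cited trials are not available to check.

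The error figures depend on the starting point. With 40% CR plus 5 points of CRi, 45% is exactly right. The 33.4% at 55% would also arise with no mismatch of labels, simply because 45% lies inside the 40-55% range. Both points stand, so the figures show sensitivity to the benchmark and not a demonstrated bias.

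The general descriptive rules (8.1.4.1, carried into phase II by 8.2.4.1) would probably yield a count of CR, since CR, CRi and CRp are defined separately. That is fair. Those rules do not, however, give CR alone a confidence interval or a role in reading the result.

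Counting missing assessments as failures (8.2.4.2) is conservative for missing data but does not put the benchmark on the right scale. Nor can the matter be left to the SAP: the null and its justification are fixed in the protocol and determine the sample size and cut-off.

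**Conclusion.** The point holds as a gap in justification. The endpoint and null are CR/CRi, all salvage figures are labelled CR, and nothing shows how 45% was drawn from 40-55% or on which scale.

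A reader might go further and conclude that the 5% error rate fails. It does not for the hypothesis as written, where the level is 4.15%. Only the inference against standard salvage is exposed, and only if its true CR/CRi rate is above about 45.7%. Across assumed rates of 45%, 50% and 55%, the chance of a false pass is 4.2%, 14.0% and 33.4%. The CRi share behind those rates is an assumption, since the documents give none.

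**What to change.** 1. In 8.2.1 and the synopsis, state for each cited study whether its rate is CR or CR/CRi, and justify 45% on the CR/CRi scale. Use one label for the 65%.
2. If 45% proves to be a CR-only rate, either restate the benchmark with the resulting cut-off and power (step 4 gives the scale), or say that rejecting 45% on CR/CRi does not by itself show an advantage over standard salvage.
3. In 8.2.3.2 and 8.2.5.2, add the CR rate alone at V8 in the FAS, with missing counted as failure and a two-sided 95% Clopper-Pearson interval. Read it only against historical rates confirmed as CR only; otherwise it would create the opposite mismatch.

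The cost is a short re-reading of the cited studies, some protocol wording and one table row from data already collected at V8. The CR-only figure cannot exceed the CR/CRi figure and will look less favourable if any responder is CRi. If the benchmark has to rise, the cost is lower power at 42 patients or a larger sample.

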### **8.2.2 Analysis sets**

#### **8.2.2.1 Full analysis set (FAS)**

The FAS consists of all patients with exposure to venetoclax and cytarabine with the MTD (including patients who received MTD in phase I part, even if they were excluded from the MTD analysis set).

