## 3 Study design

### 3.1 Design overview

This is an open-label Phase I dose-escalation study of oral venetoclax in combination with increasing cytarabine doses plus mitoxantrone to define the safety profile and MTD of cytarabine in subjects with a histologically or cytologically confirmed acute myeloid leukemia who are refractory or suffered a relapse. This study will be conducted at multiple centers in Germany.

This study will investigate the combination of a fixed maximum venetoclax dose with increasing cytarabine doses plus mitoxantrone in a fixed dose. The venetoclax dose of 400 mg will be reached by a ramp up over 4 days (see Table 2). Parallel chemotherapy with cytarabine will start on day 4. This dose escalation part will enroll a maximum number of 18 patients.

The decision to escalate to the next dose level will be taken by telephone conferences (safety calls) with participation of the investigators, pharmacovigilance and the sponsor (steering committee) on a regular basis.

AbbVie as the manufacturer of venetoclax shall be consulted in the process of decision making for continuation of the trial.

The dose-escalation part may be followed by an expansion part with enrollment of 42 patients. The decision to proceed to the expansion part will be taken and documented in consultation within

the steering committee after consideration of all available study data during the dose escalation part of the study. These results of data to safety and tolerability of the therapy during the escalation part will be submitted as a substantial amendment to the competent authority and ethics committee for approval the recommended phase-2 dose (RP2D). Patients who achieve a CR/CRp ( $ANC \geq 1 \times 10^9/L$ ) may receive venetoclax maintenance treatment at 400 mg QD p.o. continuously for up to one year. Dose reduction rules will be defined in case toxicities occur. Patients eligible for allogeneic stem cell transplantation with a suitable donor can proceed to transplantation and will be excluded from further study therapy but will further be observed during follow-up period.

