#### **Reasons for patient's premature end of study might be:**

- At their own request or at the request of their legally acceptable representative
- If, in the investigator's opinion, continuation of study would be harmful to the subject's wellbeing or if the subject is no longer eligible for the study (e.g. development of any intercurrent illness).
- At specific request of the sponsor and in liaison with the investigator (e.g. obvious non-compliance, safety concerns)
- Use of illicit drugs or other substances abuse that may, in the opinion of the investigator, have a reasonable chance of contributing to toxicity or otherwise confound the results
- Subjects who experience a relapse or are diagnosed with resistant disease throughout the trial, unless the investigator (in consultation with the sponsor) deems that continued treatment is appropriate.
- The development of a second malignancy that requires a different treatment
- Interruption of venetoclax >28 days during maintenance therapy

A withdrawn subject is referred to as either "screening failure" or "dropout (= premature end of treatment)" depending on the time point of withdrawal.

A subject who discontinues study treatment prematurely for any reason is defined as a “dropout” if the subject has already been administered at least 1 dose of the study drug. Data of drop-out patients will be analyzed intention-to treat as part of the full analysis set (FAS), see [section 8.2.2.1](#).

A subject who, for any reason (e.g. failure to satisfy the selection criteria), terminates the study prior to the first dose of study drug is regarded as a “screening failure”.

In all cases, the reason for withdrawal must be recorded in the electronic case report form (eCRF) and the subject’s medical record. If a patient has withdrawn his consent, it has also to be documented in the subject’s medical record whether the patient has agreed to further documentation of personal data during follow-up period.

Treatment with the Investigational medicinal product (IMP) venetoclax should be stopped for the following reasons and has to be reported in the appropriate page of the eCRF:

- Severe allergic reactions, such as exfoliate erythroderma, anaphylaxis, or vascular collapse, related to the study drug
- Experience of DLT
- Subjects with a beta human chorionic gonadotropin test consistent with pregnancy. Pregnancy will be reported along the same timelines as SAEs (see [section Reporting of SAEs and SARs](#)).

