## 5 Study treatment

### 5.1 Investigational medicinal product (IMP) venetoclax

#### 5.1.1 Description of the IMP

The study drug provided is venetoclax. The study drug will be supplied as 10mg, 50 mg and 100 mg film coated tablets in blisters or bottles. See current Investigator's Brochure for further characteristics, mechanism of action, preclinical activity, side effects, pharmacokinetics and results of clinical trials.

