## 5.2 Cytarabine

Commercially available cytarabine will be given and provided locally.

For information on the formulation, packaging, and handling of cytarabine see the summary of product characteristics (SmPC) for cytarabine as used in standard practice.

Cytarabine will be defined as Investigational medicinal product (IMP) for Phase I/ Escalation Phase only, in Phase II/ Expansion Phase, it will be given as concomitant medication.

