### Venetoclax

**Day 1 of venetoclax will define the study treatment start.** To mitigate the potential risk of TLS, venetoclax administration will start with a pre-specified dose ramp-up to reach the target dose level of 400 mg at day 4 (refer to Table 2).

Table 2: Venetoclax ramp up

Day	Venetoclax dose
1	50 mg
2	100 mg
3	200 mg
4 – 14 (10)*	400 mg

\* Venetoclax will be administered until day 14, only at dose level -1, venetoclax will be given until day 10.

Each dose of venetoclax should be taken with approximately 240 ml of water within 30 minutes after the completion of a meal, preferably breakfast. The dose should be administered at the same time each day. On days with planned cytarabine administration, venetoclax must be given prior to cytarabine and mitoxantrone. If a patient develops any lab changes suggestive of TLS within the first 24 hours after either first dose or during ramp up, venetoclax should be withheld until normalization of lab changes. Venetoclax will be administered in Phase I and II no longer than 10/14 days except during maintenance therapy.

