#### 8.2.4.2 Missing values

Primary endpoint: The number and proportion of missing values will be reported. Missing values can occur - for example – in the following cases:

- A patient dies before remission assessment
- A patient withdraws consent before remission assessment and does not allow collection of follow-up data
- Remission assessment is not done due to other reasons (with or without withdrawal from study treatment)
- Remission assessment is done but no valid result is available (punctio sicca, etc.)

In all cases the missing outcome is treated as failure to achieve CR/CRi. This strategy is considered to be conservative, because it can only result in underestimation of efficacy, making it harder to reject the null hypothesis.

For all other endpoints and variables the number and proportion of missing values will be reported.

Even if the patient has not been treated according to protocol or has interrupted his/her study treatment prematurely, as many endpoints as possible should be assessed. Drop-out from treatment does not mean drop-out from follow-up!

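### The FAS definition in 8.2.2.1 drops patients who exit before cytarabine starts on day 4, while 4.4.1 assigns the same patients to the FAS by intention to treat

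*Protocol*

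**What the plan says.** Protocol 8.2.2.1 defines the primary efficacy set: "The FAS consists of all patients with exposure to venetoclax and cytarabine with the MTD". A parenthesis in the same sentence adds phase I patients who received the MTD, even those left out of the MTD analysis set.

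Protocol 4.4.1 calls a patient who stops study treatment early for any reason a dropout "if the subject has already been administered at least 1 dose of the study drug", and continues: "Data of drop-out patients will be analyzed intention-to treat as part of the full analysis set (FAS". It refers to 8.2.2.1 for the definition.

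On what counts as study drug, 5.1.1 says "The study drug provided is venetoclax". Of cytarabine, 5.2 says that "in Phase II/ Expansion Phase, it will be given as concomitant medication".

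On timing, 5.4.1 says "Day 1 of venetoclax will define the study treatment start" and 3.1 says "Parallel chemotherapy with cytarabine will start on day 4".

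The CR/CRi denominator is the whole analysis set (8.2.3.1), and efficacy is analysed in the FAS (8.2.5). Section 8.2.4.2 lists the ways in which the outcome can be missing, the first being "A patient dies before remission assessment". It counts all of them as failures and argues that this can only understate efficacy. The safety set, by contrast, requires venetoclax exposure alone (8.2.2.3). Phase II patients are not replaced (4.4.2).

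**The concern.** A patient who takes venetoclax and then dies or leaves permanently on days 1-3 receives no cytarabine. Section 4.4.1 puts that patient in the FAS and 8.2.2.1 leaves the patient out. Both cannot be followed.

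FAS membership then depends on something that happens after treatment starts and is tied to outcome. Each patient removed this way would otherwise count as a failure, so removal can only raise the estimated CR/CRi rate. The assurance in 8.2.4.2 fails for these patients because the failure rule acts only inside the FAS. If early mortality and overall survival are also analysed in the FAS, as 8.2.5 indicates, a death on days 1-3 disappears from them too, although 8.2.3.2 counts both from the first dose of study drug.

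This is the only confirmatory test in an open-label, single-arm trial. If the conflict stays, it may be settled once outcomes are known.

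**Working it through.** **1. The two sections applied to one patient (venetoclax on days 1-3, then permanent exit, no cytarabine).**

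| Rule | Result |
|---|---|
| 4.4.1 (at least one dose of study drug) | dropout, in the FAS |
| 8.2.2.1 (both drugs) | not in the FAS |
| 8.2.4.2 (missing = failure) | cannot apply once the patient is outside the FAS |
| 8.2.2.3 (venetoclax only) | in the safety set |

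The conflict follows from the text and needs no calculation. The arithmetic below only sizes it.

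**2. The plan's own figure.** Inputs from 8.2.1 and the Synopsis: p0 = 0.45, p1 = 0.65, one-sided 5%, 80% power, n = 42, rejection at 25 responders. Exact binomial:
- P(X ≥ 25 | 42, 0.45) = 0.0415
- P(X ≥ 24 | 42, 0.45) = 0.0772, so 25 is the smallest valid cut-off
- P(X ≥ 25 | 42, 0.65) = 0.8182

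The design reproduces and is not in question.

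**3. One set of data under the two definitions.** Take 24 responders among 42 dosed patients and remove k early exits:
- k = 0: 24/42, p = 0.077, not rejected
- k = 1: 24/41, p = 0.057, not rejected
- k = 2: 24/40, p = 0.0405, rejected

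The decision at 24 responders changes only from two exclusions.

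**4. Type I error for a fixed number of exclusions.** Assumptions: 42 dosed patients, a true rate of 0.45 among all of them, and k excluded patients who are all non-responders. The rate among the rest is 0.45 × 42/(42 − k). The test uses the exact cut-off c for n = 42 − k. In the last column the k patients are kept as failures and the cut-off stays at 25.

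| k | n | c | rate in the rest | excluded | kept as failures |
|---|---|---|---|---|---|
| 1 | 41 | 25 | 0.4610 | 0.040 | 0.040 |
| 2 | 40 | 24 | 0.4725 | 0.073 | 0.038 |
| 3 | 39 | 24 | 0.4846 | 0.070 | 0.036 |
| 4 | 38 | 23 | 0.4974 | 0.121 | 0.034 |

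**5. Averaged over a random number of exits.** With exit probability q per patient:

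error = Σₖ P(Bin(42, q) = k) × P(Bin(42 − k, 0.45/(1 − q)) ≥ c(42 − k))

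The result is 0.043 at q = 1%, 0.047 at 2%, 0.052 at 3% and 0.065 at 5%. With all dosed patients kept it is 0.0415 throughout. The values of q are assumed, since the protocol gives none.

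**6. Effect of the phase I parenthesis.** If 3 or 6 phase I patients were treated at the MTD (assumed), the base is 42 + 3 = 45 or 42 + 6 = 48. With two exclusions:
- base 45: n = 43, c = 26, rate 0.45 × 45/43 = 0.4709, error 0.054 (0.031 with none excluded)
- base 48: n = 46, c = 27, rate 0.45 × 48/46 = 0.4696, error 0.074 (0.044 with none excluded)

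The direction is the same. The size depends on where the discrete cut-off falls.

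**The case against.** Several points on the other side are sound.

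- **Few patients.** Only a permanent exit before any cytarabine removes someone. A reader might infer that any tumour lysis or infection on days 1-3 does so, but the protocol does not support that. Laboratory changes lead to venetoclax being withheld until they normalise (5.4.1). The expansion rules allow short interruptions (5.4.5). Patients whose venetoclax is stopped for the reasons listed in 4.4.1 stay in the trial. Section 5.4.5 also reports no tumour lysis in 94 AML subjects, and patients must be stable at the start and are in hospital during the ramp-up. Deaths and dropouts after the first cytarabine dose stay in the FAS as failures.
- **Assumed counts.** The figures 0.073 and 0.121 require exactly two or four exits. With one exit from 42 there is no inflation, and on average the error passes 5% only at an exit rate of about 3%.
- **Denominator.** A reader might infer that the FAS must fall below 42 because phase II patients are not replaced. That ignores the phase I patients whom 8.2.2.1 adds to the 42 additional patients of 3.3.
- **Status of 4.4.1.** It speaks of dropouts and refers to 8.2.2.1; it does not itself define the FAS. In effect this changes little, because patients who do not drop out receive both drugs.

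These points limit the size. They do not remove the conflict. If 8.2.2.1 governs, the intention-to-treat statement in 4.4.1 is untrue for these patients and 8.2.4.2 claims too much. Nor is the two-drug condition easily read as loose wording, since the safety set in the same section asks for venetoclax alone.

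**Conclusion.** The definition is wrong as written and should be fixed. Sections 4.4.1 and 8.2.2.1 classify the same patient differently, and following 8.2.2.1 biases the CR/CRi rate upwards and leaves the failure rule in 8.2.4.2 not fully conservative.

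The likely effect is small. On a base of 42, with excluded patients who are all non-responders, one exclusion leaves the error at 0.040; two, three and four give 0.073, 0.070 and 0.121. At assumed exit rates of 1% to 3% the average error is 0.043 to 0.052, and at 5% it is 0.065. Neither the number of exits nor the number of phase I patients at the MTD is given in the protocol.

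The stronger reading, that the 5% level is materially broken or that the result will turn on this, is not supported. It would need exit counts that the protocol does not give. The sample size and the cut-off of 25 out of 42 are correct.

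**What to change.** Reconcile 8.2.2.1 with 4.4.1. Define the FAS as all patients assigned to the MTD dose level, keeping the present inclusion of phase I patients treated at that level, who received at least one dose of venetoclax. State that an absent remission assessment counts as failure for all of them, as 8.2.4.2 intends.

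The change should not restrict the FAS to phase II enrolees, which would be a separate change to the primary population. The per-protocol set needs no change, because 8.2.2.2 already requires minimum doses of both drugs.

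The cost is a short rewording of one definition. No patients, visits or data are added. The reported CR/CRi rate may be slightly lower.
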